8.3.2 New Lesions

New lesions should be assessed and measured as they appear using RECIST 1.1 criteria (maximum of 5 lesions, no more than 2 per site, at least 10 mm in long axis (or 15 mm in short axis for nodal lesions), and recorded as New Lesions-Target (NLT) and New Lesion-Non-Target (NLNT) to allow clear differentiation from baseline target and non-target lesions.

New lesions may meet the criteria of NLT or NLNT to drive iUPD (or iCPD). However, the measurements of target lesions should NOT be included in the sum of measures of original target lesions identified at baseline. Rather, these measurements will be collected on a separate table in the case record form. These data will enable the development and testing of alternate response criteria, or further modifications of RECIST.

PD is confirmed in the New Lesion category if the next imaging assessment, conducted at least 4 weeks (but not more than 8 weeks) after iUPD confirms further progression from iUPD with either an increase of at least 5 mm in the absolute value of the sum of NLT OR an increase (but not necessarily unequivocal increase) in the size of NLNT lesions OR the appearance of additional new lesions.

Table 2: Time-point (TP) iResponse

Target Lesions*	Non-Target Lesions*	New Lesions*	Time Point Response	
			No prior iUPD**	Prior iUPD**
CR / iCR	CR	No	CR	iCR
CR/iCR	Non-CR/Non-PD Non-iCR/Non-iUPD	No	PR	iPR
PR/iPR	Non-CR/Non-PD Non-iCR/Non-iUPD	No	PR	iPR
SD/iSD	Non-CR/Non-PD Non-iCR/Non-iUPD	No	SD	iSD
iUPD with no change OR decrease from last TP	iUPD with no change OR decrease from last TP	Yes	NA	The appearance NLs confirms PD if Additional NLs or iUPD in last TP based on NLs and increase in size (≥ 5 mm for NLT or any increase for NLNT) If no change in NLs from last TP, remains iUPD
PD	Non-CR/Non-PD Non-iCR/Non-iUPD	No	iUPD	Remains iUPD unless iCPD confirmed based on further increase in sum of at least 5 mm, otherwise remains iUPD
PD	PD	No	iUPD	iCPD if further increase in previously identified*** T lesion iUPD ≥ 5 mm and / or NT lesion iUPD
PD	PD	Yes	iUPD	iCPD if further increase in previously identified T lesion iUPD ≥ 5 mm and / or NT lesion iUPD and / or size or number of new lesion
Non-iUPD	Non-iUPD	Yes	iUPD	iCPD if increase in size of previously identified new lesions or increased number of new lesion

* Using RECIST 1.1 principles. If no pseudoprogression occurs, RECIST 1.1 and iRECIST categories for CR, PR and SD would be the same.
 ** In any category.
 *** Previously identified in assessment immediately prior to this time-point (TP)
 NA = not applicable.

Table 3: iRECIST Best Overall Response (iBOR)

All patients will have their iBOR from the start of study treatment until the end of treatment classified as outlined below.

TPR1	TPR2	TPR3	TPR4	TPR5	iBOR	
CR	CR, PR, iUPD, NE	CR/iCR, iUPD, iCPD, NE	PR/iPR, iUPD, NE	iUPD	iCPD	iCR
iUPD	PR, SD, NE	CR		CR, PR, SD, iUPD, NE	SD, iUPD, iCPD, NE	iCR
iUPD	PR	PR, SD, iUPD, NE		PR, SD, iUPD, NE, cPD	PR, SD, iUPD, NE, iCPD	iPR
iUPD	SD, NE	PR		PR, SD, iUPD, NE	PR, SD, iUPD, iCPD, NE	iPR
iUPD	SD	SD, iUPD, NE		SD, iUPD, iCPD, NE	SD, iUPD, iCPD, NE	iSD
iUPD	iUPD	Anything		Anything	Anything	iCPD
iUPD	iUPD	iCPD		Anything	Anything	iCPD
iUPD	NE	NE		NE	NE	iUPD
1. Table assumes a randomized study where confirmation of CR or PR is not required. 2. NE = not evaluable that cycle. 3. Designation "I" for BOR can be used to indicate prior uPD to aid in data interpretation. 4. For patients with non-target disease only at baseline, only CR or non-CR/non-PD can be assigned at each TPR but is not shown in the table for ease of presentation.						

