5.0 PATIENT EVALUATION FLOWSHEET: PRE-TREATMENT, ON STUDY, AND AFTER TREATMENT

All patients entered on study must be evaluated according to the schedule outlined below with documentation submitted according to the schedule in Appendix IV.

Required Investigations	Pre-study (≤7 days prior to randomization)	Day 1 each cycle, and as clinically indicated	Every 12 weeks after randomization	4 weeks after completion of protocol therapy	3 month follow-up (only required for pts without confirmed PD and ongoing toxicities ¹)	6 month follow-up (required for all patients with confirmed PD)
History and Physical Exam						
Including: height, weight, BSA, performance status, clinical tumour measurements (if applicable)	X	X		X		
Blood pressure, heart rate, temperature	X	X ²		X		
Laboratory Procedures/Assessments³						
CBC, differential, platelets	X	X		X ⁴	X ⁴	
PTT, PT/INR (if on anticoagulants)	X	X		X ⁴	X ⁴	
Serum creatinine, bilirubin, AST, ALT, ALP, LDH, albumin, glucose, amylase ⁵ , lipase ⁵ , electrolytes (potassium, calcium, magnesium)	X	X		X ⁴	X ⁴	
PSA	X ⁶	X ⁷		X ⁸	X ⁸	
TSH ⁹	X	X				
Testosterone (to confirm biochemical castration only)	X					
Radiology^{10,11}						
Chest/abdomen/pelvis CT scan Other scans as necessary to document disease ¹²	X (within 28 days prior to randomization or 35 if negative)		X	X	X	
Bone Scan ^{12,13}	X (within 28 days prior to randomization or 35 if negative)		X	X	X (if positive at baseline and does not yet have confirmed PD)	
Other Investigations						
Urinalysis ¹⁴	X					
LVEF ¹⁵	X (within 28 days prior to randomization)					
Adverse Events	X	Continuously		X	X ¹	
Survival/Anti-cancer Treatment Follow-up						X
Correlative Studies (mandatory)						
Fresh tumour biopsy ¹⁶	X					
Archival Tumour Tissues	X					
Blood Collection	X ¹⁷			X ¹⁸		

footnotes on next page ...

1. Every three months thereafter to follow adverse events felt related until resolved to \leq grade 2.

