8.0 CRITERIA FOR MEASUREMENT OF STUDY ENDPOINTS

8.1 Definitions

8.1.1 Evaluable for adverse events. All patients will be evaluable for adverse event evaluation from the time of their first treatment.

8.1.2 Evaluable for response. All patients who have received at least one cycle of therapy and have their disease re-evaluated will be considered evaluable for response. Patients who exhibit objective disease progression prior to the end of cycle 1 are considered to be evaluable). Patients on therapy for at least this period and who meet the other listed criteria will have their response classified according to the definitions set out below *[Seymour 2017]*.

Response and progression will be evaluated in this study using the revised international criteria (1.1) proposed by the RECIST (Response Evaluation Criteria in Solid Tumours) committee *[Eisenhauer 2009]* as well as the modified iRECIST guidelines *[Seymour 2017]*. Investigators should note the different requirements for confirmatory scans as well as follow up for the two criteria.

See Section 10 for criteria for continuing treatment past RECIST 1.1 disease progression.

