8.2 RECIST 1.1 Response and Evaluation Endpoints

Response and progression will be evaluated in this study using the revised international criteria (1.1) proposed by the RECIST (Response Evaluation Criteria in Solid Tumours) committee, as well as Immune-Related modified RECIST criteria. Investigators should continue treatment, as appropriate, in the absence of unacceptable toxicity, until unequivocal disease progression. This is particularly important for patients in whom pseudoprogression may have occurred. Follow up response assessments must be continued until unequivocal disease progression has occurred.

8.2.1 Measurable Disease. Measurable *tumour lesions* are defined as those that can be accurately measured in at least one dimension (longest diameter to be recorded) as ≥ 20 mm with chest x-ray and as ≥ 10 mm with CT scan or clinical examination. Bone lesions are considered measurable only if assessed by CT scan and have an identifiable soft tissue component that meets these requirements (soft tissue component ≥ 10 mm by CT scan). *Malignant lymph nodes* must be ≥ 15 mm in the short axis to be considered measurable; only the short axis will be measured and followed. All tumour measurements must be recorded in millimetres (or decimal fractions of centimetres). Previously irradiated lesions are not considered measurable unless progression has been documented in the lesion.

8.2.2 Non-measurable Disease. All other lesions (or sites of disease), including small lesions are considered non-measurable disease. Bone lesions without a measurable soft tissue component, leptomeningeal disease, ascites, pleural/pericardial effusions, lymphangitis cutis/pulmonis, inflammatory breast disease, lymphangitic involvement of lung or skin and abdominal masses followed by clinical examination are all non-measurable. Lesions in previously irradiated areas are non-measurable, unless progression has been demonstrated.

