8.2.3 Target Lesions. When more than one measurable tumour lesion is present at baseline all lesions up to *a maximum of 5 lesions total* (and a maximum of *2 lesions per organ*) representative of all involved organs should be identified as target lesions and will be recorded and measured at baseline. Target lesions should be selected on the basis of their size (lesions with the longest diameter), be representative of all involved organs, but in addition should be those that lend themselves to *reproducible repeated measurements*. Note that pathological nodes must meet the criterion of a short axis of ≥ 15 mm by CT scan and only the *short axis* of these nodes will contribute to the baseline sum. All other pathological nodes (those with short axis ≥ 10 mm but < 15 mm) should be considered non-target lesions. Nodes that have a short axis < 10 mm are considered non-pathological and should not be recorded or followed (see 8.2.4). At baseline, the sum of the target lesions (longest diameter of tumour lesions plus short axis of lymph nodes: overall maximum of 5) is to be recorded.

After baseline, a value should be provided on the CRF for all identified target lesions for each assessment, even if very small. If extremely small and faint lesions cannot be accurately measured but are deemed to be present, a default value of 5 mm may be used. If lesions are too small to measure and indeed are believed to be absent, a default value of 0 mm may be used.

8.2.4 Non-target Lesions. All non-measurable lesions (or sites of disease) plus any measurable lesions over and above those listed as target lesions are considered *non-target lesions*. Measurements are not required but these lesions should be noted at baseline and should be followed as “present” or “absent”.

8.2.5 Response.

All patients will have their BEST RESPONSE from the start of study treatment until the end of treatment classified as outlined below:

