10.4 Follow-up Off Protocol Treatment

All patients will be seen at 4 weeks after completion of protocol therapy. For patients who go off protocol treatment with iCPD, and have ongoing toxicities (until resolved to \leq grade 2) and late toxicities (including second malignancies) follow-up will be required every 3 months.

For patients with no ongoing or late toxicities and have confirmed disease progression, follow-up will be required every 6 months for survival data and other anti-cancer treatment only. For patients who go off protocol treatment with CR/ICR, PR/iPR, SD/iSD or iUPD ongoing, and have not already started other systemic therapy follow-up will be required every 3 months until relapse (see Section 5.0 for investigations to be performed) and then every 6 months until death.

Death Report will be required for all patients, due within 2 weeks of knowledge of death (see Appendix IV - Documentation for Study).

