13.2 Primary Endpoints and Analysis

The primary endpoint of this study is the objective response rate, using iRECIST criteria defined in Section 8. Objective response rate using RECIST 1.1 will also be reported. 95% confidence interval for objective response rate in both definitions will be calculated.

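### The best-response window closes at an undefined end of treatment, so a response first seen on an off-treatment scan is left out of the primary ORR

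*Combined protocol and SAP*

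**What the plan says.** **Endpoint.** Section 13.2: "The primary endpoint of this study is the objective response rate, using iRECIST criteria defined in Section 8". RECIST 1.1 response is reported alongside it. Section 13 gives no observation window of its own, so the window comes from section 8.

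**Window.** Table 3 (section 8.3): "All patients will have their iBOR from the start of study treatment until the end of treatment classified as outlined below". Section 8.2.5, for RECIST 1.1: "All patients will have their BEST RESPONSE from the start of study treatment until the end of treatment classified as outlined below". Neither says whether treatment ends at the last dose, at the end of the last cycle or at the 4-week visit.

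**Assessment after treatment.** Section 8.2: "Follow up response assessments must be continued until unequivocal disease progression has occurred". Section 10.4 covers patients who stop with response, stable disease or unconfirmed progression and who "have not already started other systemic therapy follow-up will be required every 3 months until relapse"; it refers to section 5.0 for the tests. The section 5.0 flowsheet marks CT at 4 weeks after therapy and in the column headed "3 month follow-up (only required for pts without confirmed PD and ongoing toxicities". That heading could be read as also requiring ongoing toxicity, but section 10.4 and Appendix IV set no such condition for patients without progression.

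**Evaluability.** Section 8.1.2: "All patients who have received at least one cycle of therapy and have their disease re-evaluated will be considered evaluable for response". It does not say that the re-evaluation must take place on treatment.

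**Scan timing.** Section 5.0 schedules CT every 12 weeks from randomization. Footnote 10 asks for a repeat scan 4 to 8 weeks after a response under either criterion.

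**Decision rule.** Section 13.3: 12 patients per arm, continue with at least 1 response, expand to 37 evaluable, and go forward with at least 4.

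**The concern.** Unacceptable toxicity is a listed reason to stop treatment without progression (section 10.1). Such a patient is still scanned, and the scan may show a response, but the stated window has closed. Two groups are affected:

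- patients who stop before week 12 and so have no scheduled scan on treatment;
- patients scanned on treatment whose first partial or complete response appears only after stopping and before any new therapy.

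Both can take up one of the 37 evaluable places, while their response cannot enter the numerator. The error runs in one direction only, and the thresholds are low enough for a single patient to matter: 1/12 becomes 0/12, or 4/37 becomes 3/37. If the window is interpreted only after such a patient has appeared, the choice is made with the outcome known.

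**Working it through.** **1. Timing.** A cycle is 4 weeks and the first scheduled scan is at week 12, that is, after three cycles. A patient who stops after two cycles ends the last cycle at 2 × 4 = week 8. Appendix IV places the 4-week post-treatment report 4 weeks after the end of the last cycle, so at about week 12. This patient's first scheduled scan therefore falls inside or outside the window according to how end of treatment is understood. The 3-month follow-up scans fall outside on any ordinary reading, because Appendix IV ties the End of Treatment Report to going off protocol treatment and lists the later reports separately.

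**2. Reproducing the design.** Inputs from section 13.3: p0 = 0.05, p1 = 0.20, alpha 0.1, beta 0.1, n1 = 12, N = 37. With X1 responses in the first 12 and X2 in the next 25,

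P(go) = P(X ≥ 4 of 37) − P(X1 = 0) × P(X2 ≥ 4 of 25).

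- At p = 0.20: 0.9550 − 0.0687 × 0.7660 = 0.902 (power).
- At p = 0.05: 0.1119 − 0.5404 × 0.0341 = 0.0935 (type I error).

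A search over two-stage designs for the smallest expected sample size under the null returns the same 0/12, 3/37 boundaries. The design is correctly stated.

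**3. Effect of the window.** Let f be the share of true responses that the window excludes, with those patients kept in the denominator. The scored rate is then p(1 − f). The documents give no value for f, so every row below except f = 0 is an assumption.

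| f | Scored rate if true rate is 20% | P(0/12) = (1 − rate)^12 | P(go) |
|---|---|---|---|
| 0 | 0.20 | 0.069 | 0.902 |
| 5% | 0.19 | 0.080 | 0.882 |
| 10% | 0.18 | 0.092 | 0.857 |
| 20% (upper illustration) | 0.16 | 0.123 | 0.792 |

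At a true rate of 5%, the type I error falls from 0.093 to 0.070 (f = 10%) or 0.049 (f = 20%).

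**4. One patient at the final boundary.** 4/37 = 10.8% (exact 95% CI 3.0% to 25.4%) passes. 3/37 = 8.1% (1.7% to 21.9%) does not.

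**5. Confirmation, text against text.** Section 8.2.5 requires confirmation of complete and partial response under RECIST 1.1. Note 1 to Table 3 assumes that confirmation is not required for iBOR. Footnote 10 in section 5.0 asks for repeat scans under both. So a partial response at week 12, with treatment stopped before the repeat scan 4 to 8 weeks later (weeks 16 to 20), is clearly at risk only in the RECIST 1.1 rate.

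**The case against.** The other side has a fair case on five points.

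- **The two end dates need not conflict.** Off-treatment scans also serve response duration (section 8.4), time to progression and confirmation of unconfirmed progression. An on-treatment best response is a coherent and conservative choice. This stands: the later scans do not show that the window is an error. They show that the data needed for the wider definition are already collected.
- **Automatic non-response.** A reader might infer that these patients must be scored as non-responders. The documents do not settle this. The result could be not evaluable, and the 4-week scan might count as on treatment. If early stoppers were instead treated as not evaluable and replaced, the loss in step 3 would be smaller. In no case is a response first seen at a 3-month scan credited.
- **Late confirmation.** A reader might infer that the primary endpoint also loses responses first seen on treatment but confirmed after it. Note 1 to Table 3 tells against that, and nothing requires the confirming scan to fall inside the window.
- **Size.** A reader might take 20% as the expected loss because section 2.0 reports grade 3/4 related events in 4/18 patients on the combination. Those are not discontinuations: only one of the 18 stopped for drug-related events. Even 1/18 (5.6%) counts stopping at any time, not responding afterwards.
- **Closing an arm.** Section 13.3 allows a PD-L1-positive expansion to be considered after 0/12 or after fewer than 4 responses, so a missed threshold need not end an arm. Nor does a possibly larger loss in the combination arm distort a comparison, since the design is non-comparative.

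**Conclusion.** The point holds as a gap in the definition of the primary endpoint and should be fixed. Taken literally, sections 8.2.5 and 8.3 give no credit for a response first documented after treatment ends, whether the patient is scored not evaluable or non-responding, and the meaning of end of treatment is left open. The bias is downward only. With 5% to 10% of responses lost, power at a true 20% rate falls by 2 to 4.5 percentage points (0.902 to 0.882 or 0.857), and the false stage-1 stop rises by 1.1 to 2.4 points (6.9% to 8.0% or 9.2%). These figures rest on an assumed share of lost responses and on the affected patients staying in the denominator; the 20% row only marks an upper illustration. The average effect is modest, but the thresholds are low enough for one patient to change an arm's result, so the rule should be fixed before the data are read.

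**What to change.** In section 8.2.5 and Table 3, repeated in section 13.2:

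- iBOR runs from the start of study treatment until confirmed progression (iCPD), start of new anticancer therapy or death, whichever comes first.
- RECIST 1.1 best response runs from the start of study treatment until first progression, new anticancer therapy or death, whichever comes first.
- The scheduled 4-week and 3-month follow-up scans count towards both.
- A confirmatory scan after the last dose and before new therapy is valid. Reconcile section 8.2.5, note 1 to Table 3 and footnote 10 on whether iRECIST responses need confirmation.
- Define end of treatment, and report the on-treatment-only response rate as a sensitivity analysis.

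**Cost.** A few sentences and one extra analysis; no new visits, scans or patients. The conservatism of the present window is given up: the type I error returns to its design value of 0.093, still below 0.10.

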2. Patients will be monitored before, during and after the first cycle infusion of tremelimumab and durvalumab with assessment of vital signs to be collected \leq 30 minutes prior to start of infusion then every 30 \pm 5 minutes during infusion; a 1-hour observation period is recommended after the tremelimumab. Assessment of vital signs in subsequent cycles is required prior to the start of the infusion, and then as clinically indicated. If no clinically significant infusion reactions are observed during or after the first cycle of tremelimumab+durvalumab therapy, subsequent infusion observation periods can be at the investigator's discretion.
3. Pre-treatment blood draws and physical exams may be done one working day prior to treatment if necessary (e.g. Friday for treatment on Monday, or to accommodate holidays). In order to ensure that nadir counts are not missed, every effort should be made to do interim blood draws within 24 hours of the day specified in the protocol. If a patient shows an AST or ALT $\geq 3 \times$ ULN together with total bilirubin $\geq 2 \times$ ULN, refer to Appendix II for further instructions on cases of increases in liver biochemistry and evaluation of Hy's Law. These cases should be reported as SAEs if, after evaluation, they meet the criteria for a Hy's law case or if any of the individual liver test parameters fulfill any of the SAE criteria.
4. Required at 4 weeks. Then every 3 months thereafter to follow abnormal lab results felt related until resolved to \leq grade 2.
5. It is preferable that both amylase and lipase parameters are assessed. For sites where only 1 of these parameters is routinely measured then either lipase or amylase is acceptable as long as the same one is followed throughout.
6. At least three previous PSA values with the interval between of ≥ 4 weeks, should be recorded for the patient to estimate doubling time as well as one prior to registration.
7. PSA should also be done at the end of the last cycle.
8. All patients at 4 weeks. For patients without PSA progression, repeat every 4 to 8 weeks until progression or until new systemic therapy is initiated.
9. Free T3 and free T4 will be measured if TSH is abnormal.
10. Patients with CR/iCR or PR/iPR or equivocal PD (pseudoprogression)/iUPD should have scans repeated after 4 weeks, but no more than 8 weeks, to confirm response.

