Complete Response (CR): disappearance of *target* and *non-target* lesions and normalization of tumour markers. Pathological lymph nodes must have short axis measures < 10 mm (Note: continue to record the measurement even if < 10 mm and considered CR). Residual lesions (other than nodes < 10 mm) thought to be non-malignant should be further investigated (by cytology specialized imaging or other techniques as appropriate for individual cases [Eisenhauer 2009]) before CR can be accepted. Confirmation of response is required in this small randomized control trial.

Partial Response (PR): at least a 30% decrease in the sum of measures (longest diameter for tumour lesions and short axis measure for nodes) of target lesions, taking as reference the baseline sum of diameters. Non target lesions must be non-PD. Confirmation of response is required in this small randomized control trial.

Stable Disease (SD): Neither sufficient shrinkage to qualify for PR nor sufficient increase to qualify for PD taking as reference the smallest sum of diameters on study.

Progressive Disease (PD): at least a 20% increase in the sum of diameters of measured lesions taking as references the smallest sum of diameters recorded on study (including baseline) AND an absolute increase of $\geq 5\text{mm}$. Appearance of new lesions will also constitute progressive disease (including lesions in previously unassessed areas). In exceptional circumstances, unequivocal progression of non-target disease may be accepted as evidence of disease progression, where the overall tumour burden appears to have increased by at least 73% in volume or, in select instances where tumour burden has increased sufficiently to require urgent medical intervention (e.g. radiation for spinal cord compression or drainage of a fluid collection. Modest increases in the size of one or more non-target lesions are NOT considered unequivocal progression. If the evidence of PD is equivocal (target or non-target), treatment may continue until the next assessment, but if confirmed, the earlier date must be used.

Patients that are clinically well may continue on therapy following RECIST progression with new lesions or increase in target lesions if the increase in disease burden does not meet the definition of PD by immune response criteria [Seymour 2017]. In this situation, patients do not have unequivocal progression until immune response criteria are met (see Table 2 below).

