Table 1: Integration of Target, non-Target and New Lesions into Response Assessment:

Target Lesions	Non-Target Lesions	New Lesions	Overall Response	Best Response for this Category also Requires
Target lesions \pm non target lesions				
CR	CR	No	CR	Normalization of tumour markers, tumour nodes $< 10\text{ mm}$
CR	Non-CR/Non-PD	No	PR	
CR	Not all evaluated	No	PR	
PR	Non-PD/ not all evaluated	No	PR	
SD	Non-PD/ not all evaluated	No	SD	Documented at least once ≥ 4 wks. from baseline
Not all evaluated	Non-PD	No	NE	
PD	Any	Any	PD	
Any	PD	Any	PD	
Any	Any	Yes	PD	
Non target lesions ONLY				
No Target	CR	No	CR	Normalization of tumour markers, tumour nodes $< 10\text{ mm}$
No Target	Non-CR/non-PD	No	Non-CR/non-PD	
No Target	Not all evaluated	No	NE	
No Target	Unequivocal PD	Any	PD	
No Target	Any	Yes	PD	
Note: Patients with a global deterioration of health status requiring discontinuation of treatment without objective evidence of disease progression at that time should be reported as "symptomatic deterioration". This is a reason for stopping therapy, but is NOT objective PD. Every effort should be made to document the objective progression even after discontinuation of treatment.				

8.3 iRECIST Response Assessment

Overall response will also be assessed using iRECIST [Seymour 2017]. Immunotherapeutics may result in infiltration of immune cells leading to transient increase in the size in malignant lesions, resulting in previously undetectable lesions becoming detectable. The criteria are identical to those of RECIST 1.1 in many respects but have been adapted to account for instances where an increase in tumour burden, or the appearance of new lesions, does not reflect true tumour progression.

Key differences are described below. All responses defined using iRECIST criteria are designated with a prefix. iRECIST time-point and best overall responses will be recorded separately.

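### Primary iRECIST response rate: Table 3 lets an unconfirmed response after iUPD count, against the confirmation required in 8.2.5, and 13.3 does not say which applies to the 1/12 and 4/37 cut-offs

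*Combined protocol and SAP*

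**What the plan says.** Section 13.2 makes the objective response rate by iRECIST, as defined in Section 8, the primary endpoint. The RECIST 1.1 rate is reported alongside it.

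Section 8.2.5 says under both CR and PR: "Confirmation of response is required in this small randomized control trial". It stands under the RECIST 1.1 heading, but the opening sentence of 8.2 covers RECIST 1.1 "as well as Immune-Related modified RECIST criteria".

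Section 8.3 introduces iRECIST with "Key differences are described below". The differences that follow concern confirming progression (8.3.1) and new lesions (8.3.2). Table 3 then sets best overall response: "All patients will have their iBOR from the start of study treatment until the end of treatment classified as outlined below". Its note 1 reads: "Table assumes a randomized study where confirmation of CR or PR is not required".

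Three other places bear on the question:
- Section 5.0, footnote 10: patients with CR/iCR or PR/iPR "should have scans repeated after 4 weeks, but no more than 8 weeks, to confirm response".
- Table 2 footnote: "If no pseudoprogression occurs, RECIST 1.1 and iRECIST categories for CR, PR and SD would be the same".
- Section 8.1.2: "Investigators should note the different requirements for confirmatory scans as well as follow up for the two criteria".

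Section 13.3 expands an arm on at least 1 response in 12 and considers it for phase III on at least 4 in 37. It does not say whether these responses are confirmed.

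**The concern.** Sections 8.2.5 and Table 3 start from the same feature, that the trial is randomized, and reach opposite rules. Table 3 is the operative table for the primary endpoint, and its rows follow its note. The sequence iUPD, then SD or NE, then PR, then SD is classed iPR, as is iUPD, then PR, then SD. One qualifying scan is enough.

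The trial is non-comparative (13.1) and each arm is judged against a fixed 5%, so no between-arm contrast offsets unconfirmed responses. Zero or one response in 12 decides whether an arm expands and, under 6.2, whether randomization continues to two cohorts or one. Three or four in 37 decides whether an arm is considered for phase III. The treatment is open-label, so a rule left unsettled could end up being chosen with the responses already known.

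The gap between the two reported response rates is also affected. It should reflect responses after apparent progression, but would also include responses that were never confirmed.

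**Working it through.** **1. The plan's own design.** Inputs from 13.3: null rate 0.05, target rate 0.20, alpha and beta 0.1, 12 patients at stage 1, 37 in total, continue on at least 1, positive on at least 4. The chance that an arm is declared positive at true counted rate p is

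go(p) = Σ (x = 1 to 12) Bin(x; 12, p) × P[Bin(25, p) ≥ 4 − x].

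At p = 0.05 the terms are:
- x = 1: 0.3413 × 0.1271 = 0.0434
- x = 2: 0.0988 × 0.3576 = 0.0353
- x = 3: 0.0173 × 0.7226 = 0.0125
- x ≥ 4: 0.0022

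The unrounded sum is 0.0935. At p = 0.20, go = 0.9024. The chance of stopping an inactive arm at stage 1 is 0.95^12 = 0.540. A search over two-stage designs returns 0/12 and 3/37 as the optimal one. The design is reproduced and meets its stated error rates, provided one definition of response serves both the rates and the counts.

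**2. One patient under the two passages.** Take the sequence iUPD, SD, PR, SD. Under 8.2.5, read as covering the whole trial, the PR is not confirmed and counts 0. Under Table 3 the patient is iPR and counts 1. If this is the arm's only response among the first 12, the same scans give 0/12 (threshold missed) or 1/12 (expand).

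**3. Effect on the false-go rate, post-iUPD responses only.** Suppose 5% is a confirmed rate and Table 3 is followed. Let s be the share of confirmed responses that come after iUPD, and f the share of post-iUPD responses that would fail confirmation. Neither is in the documents; both are assumed. The counted rate is

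p = 0.05 × (1 − s + s/(1 − f)).

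| f | s = 10%: p | go(p) | s = 20%: p | go(p) |
|---|---|---|---|---|
| 10% | 0.0506 | 0.096 | 0.0511 | 0.099 |
| 25% | 0.0517 | 0.102 | 0.0533 | 0.111 |
| 50% | 0.0550 | 0.121 | 0.0600 | 0.151 |

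go(p) reaches 0.10 at p = 0.05125, which is s × f/(1 − f) = 0.025. That is f = 20% when s = 10%, and f = 11% when s = 20%.

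**4. Outer case, unconfirmed responses counted for every patient.** The counted rate is 0.05/(1 − f):
- f = 10%: p = 0.0556, go = 0.124
- f = 20%: p = 0.0625, go = 0.167

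**The case against.** The best defence is that the intended rule can be inferred. Note 1 states a generic assumption, whereas 8.2.5 speaks of this trial. Footnote 10 names iCR and iPR and orders a repeat scan for confirmation. The Table 2 footnote makes the response categories identical when there is no pseudoprogression. The differing scan requirements mentioned in 8.1.2 are explained in 8.3.1 as concerning progression. The consequences are also softened: an arm that succeeds is only considered for phase III, and an arm that misses either threshold may still be expanded in PD-L1-positive patients.

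All of this stands, and it narrows the point. It does not remove it. Footnote 10 schedules scans but does not say how an unrepeated iPR is scored. The table that classifies patients scores it as a response, and 13.3 does not choose between them.

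A reader might go further and infer that every response may count unconfirmed, giving the 0.124 and 0.167 of step 4. The documents do not support that. The legible single-scan rows all start with iUPD, and the first row, for an initial CR, is too broken in the available text to carry weight. No row starts with PR, so a responder without prior iUPD falls to the Table 2 footnote and thus to the RECIST 1.1 category, where confirmation is required. Nor does 8.1.2 show that iRECIST was meant to waive confirmation of response.

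**Conclusion.** The conflict is real, touches the primary endpoint and should be fixed before the stage 1 look. Confirmation is the probable intent, and note 1 with its rows appears to have been left unadapted. Followed as written, however, Table 3 yields a count that 8.2.5 would not allow.

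The certain part of the effect is that one post-iUPD patient can change either decision. The size in error-rate terms depends on two unknowns. Over the ranges assumed, the false-go rate runs from 0.096 to 0.151 against a limit of 0.10, and at 10% failing it stays within the limit. These figures assume that 5% was meant as a confirmed rate, which 13.3 does not state.

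It might also be inferred that the sample size or the Simon boundaries are wrong. They are not: the stated design reproduces exactly. This is a defect in the endpoint definition.

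**What to change.** 1. In 13.2 and 13.3, state that the primary iRECIST response rate and the 1/12 and 4/37 counts use responses confirmed on the footnote 10 repeat scan, and that 5% and 20% are rates on that definition.
2. Replace note 1 of Table 3 and align the rows that give iCR or iPR on a single scan. Report the unconfirmed rate as supportive.
3. State that an arm whose only response is awaiting its repeat scan at the stage 1 look is not decided until that scan is read. State also whether accrual and allocation to that arm pause meanwhile, since 6.2 provides only for two enrolling cohorts or one closed.
4. If the sponsor instead intends unconfirmed responses to count, say so in 13.3, define 5% and 20% on that basis, and reconcile 8.2.5 and footnote 10.

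Cost: the repeat scans are already scheduled, and sample size and cut-offs stand if 5% and 20% are confirmed rates. The reported rate may be slightly lower. The stage 1 decision may wait 4 to 8 weeks (week 16 to 20 rather than week 12 for a response first seen on the first 12-week scan), and only when the arm has no response already confirmed.
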